Synopsis and Section 9.1: Inclusion Criterion #8.	Adjusted levels of total cholesterol, HDL, LDL and triglycerides in inclusion criteria to better reflect the healthy population at large. This adjustment is not expected to impact subject safety.

Protocol Sections	Changes Made in Version 5.1 from Version 5.0
Title page, synopsis	Principal Investigator changed from [name], MD to [name], MD.

Protocol Sections	Changes Made in Version 5.0 from Version 4.0
Synopsis, Sections 6.3, 8.1, 8.3, and 11.3 (Table 4)	Based on the FDA's comments to follow Fibonacci sequence for dose escalation, the dose escalation scheme has been updated to 3, 6, 10, and 13 mg/m ² . and provided rationale for starting dose of 3 mg/m ² ,
Section 10.6	Per FDA comments, an AUC limit/cap of 16550 ng•hr/mL (i.e. escalation to the next dose should not proceed if the expected AUC will exceed 16550 ng•hr/mL). The limit is based on the mean AUC

	of male and female monkeys at the NOAEL (3 mg/kg) in the 28-day toxicity study.
--	---

Protocol Sections	Changes Made in Version 4.0 from Version 3.0
Synopsis, Sections 8.1, and 8.3	Based on the FDA's comments to follow Fibonacci sequence for dose escalation, the dose level for Cohort 4 has been reduced from 65 mg/m ² to 55 mg/m ²
Synopsis and Section 9.1	Per FDA recommendation, adjusted inclusion criterion #8 from: Have clinical laboratory renal (eGFR, creatinine) and liver (AST, ALT, GGT, Total bilirubin) function within normal range (eGFR \geq 90 mL/min/1.73 m ²) and other clinical laboratory results within normal range or outside normal range assessed as clinically non-significant by the Investigator at screening and admission To: Have clinical laboratory renal (eGFR, creatinine) and liver (AST, ALT, GGT, Total bilirubin) function within normal range (eGFR \geq 90 mL/min/1.73 m ²) and other clinical laboratory results within normal range or within 5% of normal range and assessed as clinically non-significant by the Investigator at screening and admission

Protocol Sections	Changes Made in Version 3.0 from Version 2.0
Synopsis, Sections 8.1, and 8.3	Based on the FDA's comments to follow Fibonacci sequence for dose escalation, the dose level for Cohort 4 has been reduced from 90 mg/m ² to 65 mg/m ²
Synopsis and Section 9.2	Per FDA recommendation to exclude subjects with QTc > 450ms. Exclusion criterion #5 updated from "Reported family history of long QTc syndrome" to "Reported family history of long QTc syndrome or a QTc of > 450 ms at screening."
Synopsis and Section 9.1	Per FDA recommendation, addition of eGFR cutoff value of \geq 90 mL/min/1.73 m ² to inclusion criterion #8.
Table 1: Schedule of Procedures	Per FDA recommendation triplicate ECGs are included at baseline (pre-dose) and at 1.5 h post start of infusion.

Protocol Sections	Changes Made in Version 2.0 from Version 1.0
Section 10.6	Based on the FDA's comments to update DLT definitions to: a. Specify that any one grade \geq 3 AE will halt dose escalation unless the AE is clearly and incontrovertibly due to extraneous causes.

	
b. Specify that any two grade ≥ 2 AEs will halt dose escalation unless the AEs are clearly and incontrovertibly due to extraneous causes.
 
c. Grade 3 asymptomatic laboratory abnormalities that resolved to \leq grade 1 within 3 days may be excluded from the definition of DLT.

Synopsis and Section 9.1	Updated inclusion criteria #8 based on the FDA's comments to provide details regarding renal and hepatic function. Renal function will be assessed according to laboratory results of eGFR and creatinine within normal ranges and liver function shall be assessed according laboratory results of ALT, AST, GGT, and total bilirubin within normal ranges.
Table 1 Schedule of Procedures and Section 13.1.2	Updated per FDA recommendation to monitor infusion reactions by obtaining vital signs every 15 mins for the first hour and every 30 minutes through 1-hour post infusion (2 hours post start of infusion).

2 SYNOPSIS

Name of Sponsor/Company: HighField Biopharmaceutical Corporation	
Name of Investigational Product: HF1K16	
Name of Active Ingredient: (2E,4E,6E,8E)-3,7-dimethyl-9-(2,6,6-trimethylcyclohexen-1- yl)nona-2,4,6,8-tetraenoic acid	
Title of Study: A Phase 1, Randomized, Double-Blind, Placebo-Controlled, Sequential Parallel Group, Single Ascending Dose Study Following Intravenous Administration of HF1K16 in Healthy Subjects to Evaluate the Safety, Tolerability and Pharmacokinetics of HF1K16	
Study center(s): Frontage Clinical Services, Inc.	
Principal Investigator: [name]	
Studied period (years): Estimated date first subject enrolled: TBD Estimated date last subject completed: TBD	Phase of development: Phase 1
Objectives: Primary: 
To evaluate the safety and tolerability of HF1K16 following single ascending doses by intravenous administration. Secondary: 
To characterize the pharmacokinetics of HF1K16 following single ascending doses by intravenous administration.	
Methodology: This is a randomized, double-blind, placebo-controlled, dose escalation study to evaluate the safety, tolerability and pharmacokinetics (PK) of HF1K16 following single ascending dose administration by intravenous (IV) infusion in healthy adult volunteers. Up to 4 dose cohorts are planned. The HF1K16 dose level of each cohort is determined based on the collective nonclinical data of HF1K16 (pharmacology and toxicology). The starting dose of 3 mg/m ² of HF1K16 represents about a 10-fold safety margin based on a body surface area-adjusted dose at the no-observable-adverse-effect level (NOAEL) dose of 10 mg/kg [human equivalent dose (HED): 3 mg/kg] after HF1K16 was administered IV to cynomolgus monkeys once every two days for a total of 14 doses in a 28-day dosing period, and takes into consideration exposure values following oral Vesanoid at the recommended human dose of 45 mg/m ² /day. The starting dose was selected in accordance with scientific standards outlined in the Food and Drug Administration (FDA) Guidance for Industry, "Estimating the Maximum Safe Starting Dose in Initial Clinical Trials for Therapeutics in Adult Healthy Volunteers" (July 2005). The proposed dose levels of Cohorts 1, 2, 3 and 4 are up to 3 mg/m ² , 6 mg/m ² , 10 mg/m ² and 13 mg/m ² , respectively.	

A total of up to 32 subjects will be evaluated with 24 subjects randomized to receive active drug and 8 subjects randomized to receive placebo in a double-blind fashion (8 subjects per each dose cohort, with 6 subjects randomized to receive active drug and 2 subjects randomized to receive placebo).

Following a screening period of up to 28 days, eligible subjects will be admitted to the Clinical Research Unit (CRU) on Day -1, one day prior to dosing, remain at the CRU for 3 overnight stays, and be discharged the morning of Day 3, approximately 48 hours post-dose.

Vital sign assessments will be done at screening, pre-dose and 0.5, 2, 6, 24 and 48 hours post-dose relative to the start of infusion. Clinical safety laboratory assessments will be performed at screening, on Day -1 and Day 3. A resting 12-lead electrocardiogram (ECG) will be completed at screening, Day -1, 12, 24 and 48 hours post-dose. A full physical examination will be conducted at screening, and abbreviated physical examinations will be conducted on Day -1 and Day 3. Injection site assessments will be performed prior to and 4 and 24 hours relative to the start of infusion.

A follow-up telephone call will be placed to all subjects on Day 8 (\pm 2 days) to collect adverse event (AE) and concomitant medication information.

Single dose escalation will not occur until review of the single dose safety and PK data from the previous dose cohort. After the starting dose of HF1K16, dose escalation decisions will be based on safety and tolerability assessments collected up to Day 8, and agreed upon by the Safety Monitoring Committee (SMC) comprised of, at least, the Investigator and the Medical Monitor from the Sponsor.

Number of subjects (planned):

Up to 32 evaluable healthy male and non-childbearing female subjects, 8 subjects (6 active, 2 placebo) per cohort for up to 4 cohorts.

Selection of Subjects:

Inclusion Criteria:

1. Capable of giving informed consent and complying with study procedures;
2. Between the ages of 18 and 55 years, inclusive;
3. Body mass index (BMI) of 18.0 to 32.0 kg/m² inclusive and body weight not less than 50 kg;
4. Female subjects must have a negative pregnancy test result at screening and at admission;
5. Female subjects are:
 - a. Surgically sterile for at least 3 months prior to screening by one of the following means:
 - Bilateral tubal ligation
 - Bilateral salpingectomy (with or without oophorectomy)
 - Surgical hysterectomy
 - Bilateral oophorectomy (with or without hysterectomy)
 - b. Postmenopausal, defined as the following:
 - Last menstrual period greater than 12 months prior to screening, and
 - Postmenopausal status confirmed by serum follicle stimulating hormone (FSH) and estradiol levels at screening;
6. Male subjects must agree to utilize a highly effective method of contraception (condom plus spermicide) during heterosexual intercourse from the time of clinic admission until 12 weeks following the end of study visit, and refrain from donating sperm for this same period;
7. Considered healthy by the Investigator, based on subject's reported medical history, full physical examination, 12-lead ECG, and vital signs;

8. Have clinical laboratory renal (eGFR, creatinine) and liver (AST, ALT, Total bilirubin) function within normal range and other clinical laboratory results within normal range or outside normal range assessed as clinically non-significant by the Investigator at screening and admission;
9. Non-smoker and has not been exposed to any products containing nicotine in the last 6 months;
10. Willing and able to adhere to study restrictions and to be confined at the Clinical Research Unit.

Exclusion Criteria:

1. Clinically significant reported history of gastrointestinal, cardiovascular, musculoskeletal, endocrine, hematologic, psychiatric, renal, hepatic, bronchopulmonary, neurologic, immunologic, lipid metabolism disorders, or drug hypersensitivity as determined by the Investigator;
2. Known or suspected malignancy;
3. Reported history of pancreatitis or gall stones;
4. Reported history of unexplained syncope, symptomatic hypotension or hypoglycemia;
5. Reported family history of long QTc syndrome or a QTc of > 450 ms at screening;
6. Reported history of chronic diarrhea, malabsorption, unexplained weight loss, food allergies or intolerance;
7. Poor venous access;
8. Positive blood screen for human immunodeficiency virus (HIV), hepatitis B surface antigen (HBsAg), or hepatitis C virus antibody (anti-HCV) at screening;
9. Donated or lost >500 mL of blood in the previous 3 months prior to screening;
10. Taken an investigational drug or participated in a clinical trial within 30 days (or 5 half-lives) prior to first dose of study drug, whichever is longer;
11. Taken any prescription medications within 14 days or 5 half-lives (whichever is longer) of the first dose of study drug;
12. Taken any prescription or non-prescription drugs and herbal medication known to be CYP450 inducers, inhibitors, and substrates within 14 days prior to screening (See [Appendix B](#));
13. Taken daily Vitamin A supplement within 3 months prior to screening;
14. Major surgery or hospitalization within 6 months prior to screening that in the Investigators opinion would put the subject or study conduct at risk;
15. A history of prescription drug abuse, or illicit drug use within 9 months prior to screening;
16. A history of alcohol abuse according to medical history (≥ 2 drinks per day for male and ≥ 1 drink per day for female) within 9 months prior to screening;
17. A positive screen for alcohol, drugs of abuse at screening or admission;
18. An unwillingness or inability to comply with food and beverage restrictions during study participation;
19. Use of over-the-counter (OTC) medication within 7 days, and/or herbal medications (including herbal teas, garlic extracts) within 7 days prior to first dose of study drug;
20. Have a history of allergic reactions (either spontaneous or following drug administration) to ATRA or to any of the excipients or related compounds, including vitamin A;
21. Any condition or finding that in the Investigators opinion would put the subject or study conduct at risk if the subject were to participate in the study.

Investigational product, dosage, and mode of administration:

HF1K16 is a pegylated liposome formulation of tretinoin [All-Trans Retinoic Acid (ATRA)] supplied as 2 mg/mL, 10 mL/vial. Each subject will be administered a single IV infusion of HF1K16 over a period of approximately 60 minutes.

Duration of Study:

The total duration of participation in the study for each subject is up to 38 days, including a screening period of up to 28 day.

Reference therapy:

Placebo will be sterile saline (0.9% sodium chloride) for IV infusion.

Criteria for evaluation:

Safety:

Safety assessments will include monitoring of AEs, vital signs (blood pressure, pulse rate, respiration rate, oral temperature), clinical laboratory findings (chemistry, including LDL-C, HDL-C, triglycerides, total cholesterol, AST and ALT; coagulation parameters PT/INR and aPTT; hematology and urinalysis), resting 12-lead ECGs, physical examination findings (including evaluation of skin) and injection site assessment.

Pharmacokinetics:

Pharmacokinetic analysis of the plasma concentration time data for free tretinoin and liposome encapsulated tretinoin will be performed using WinNonlin version 8.1 or higher (Certara, Princeton, NJ) and analyzed using non-compartmental methods. Actual dosing and sampling times will be used for analyses. The primary pharmacokinetics parameters of interest are: C_{max} , T_{max} , $t_{1/2}$, AUC_{last} . Additional PK parameters include AUC_{inf} , MRT, CL/F, V_zF and K_{el} .

Statistical methods and Planned Analysis:

Safety:

Adverse events will be summarized by system organ class (SOC) and preferred term (PT). A subject will only be counted once per SOC and once per PT within a treatment. Subject counts and percentages and AE counts will be presented for each treatment and totaled for all treatments. Listings will be presented by subject for all AEs.

Clinical laboratory values at each visit and change from baseline will be summarized using descriptive statistics (n, mean, median, standard deviation, minimum, and maximum). All clinical laboratory data will be presented in listings. Within each listing, laboratory values outside the normal ranges will be flagged as either high (H) or low (L).

Other safety parameters will be listed and summarized using descriptive statistics. Data from placebo-treated subjects in each cohort will be pooled for summary presentations. No formal statistical analysis of safety data is planned.

Pharmacokinetics:

Individual plasma concentrations and PK parameters of baseline-subtracted free tretinoin and liposome encapsulated tretinoin will be listed and summarized using descriptive statistics. Individual and mean free tretinoin and liposome encapsulated tretinoin concentration-time profiles will be presented graphically.

A dose proportionality regression assessment for log-transformed C_{max} , AUC_{0-t} , and AUC_{0-inf} and log-transformed dose will be analyzed using a power model: $\ln(\text{PK parameter}) = \mu + \beta \times \ln(\text{dose})$ for free tretinoin or liposome encapsulated tretinoin. The 90% confidence intervals (CI) around the slopes (β) from each of these regression analyses will be obtained from the model and presented. Plots of the log-PK parameter by log-dose (AUC_{0-t} , AUC_{0-inf} , and C_{max}) will be produced.

Statistical tables will be generated using SAS version 9.4 or higher. Disposition of all randomized subjects will be summarized by treatment and listed for each subject. Demographic and baseline characteristics will be listed and summarized for the safety population using descriptive statistics. Each subject's exposure to study drug will be listed. Adverse events will be coded using a standardized Medical Dictionary for Regulatory Activities (MedDRA), Version 23.0 or higher. Prior and concomitant medications will be coded using the World Health Organization (WHO) Drug Enhanced Dictionary (March 2020 or later). Tabulations will be prepared including all AEs and all AEs by relationship and severity using Common Terminology Criteria for Adverse Events Version 5.0 [CTCAE v5]. Adverse events resulting in early termination and events meeting regulatory criteria for seriousness will also be tabulated separately. By subject listings of all safety data and concomitant medication use will be generated.

This study will be conducted in accordance with the guidelines of Good Clinical Practices (GCPs) including archiving of essential documents.

Table 1: Schedule of Procedures

	Screen	Subjects Resident in Clinical Research Unit												FU Tel Call				
		Day	-28 to -1	-1	Day 1								2	3*	Day 8 ± 2			
Hour					0	0.25	0.5	0.75	1	1.5	2	4	6	9	12	24	36	48
Informed Consent	X																	
Eligibility Assessment	X	X																
Demographics	X																	
Admission to CRU																		
Randomization																		
Medical History																		
Physical Exam ¹																		
Height, Weight, BMI																		
Weight																		
Resting 12-lead ECG ²																		
Vital signs (BP, PR, RR, Oral Temp)																		
Clinical laboratory tests ³																		
HIV, Hep B&C screen																		
Drug/alcohol screen																		
Pregnancy test ⁴																		
FSH and estradiol ⁵																		
Dose administration ⁶																		
PK blood samples																		
Injection site assessment																		
AE & ConMeds																		
Discharge from CRU																		

NOTE: all timed procedures are with respect to START of study drug infusion.

AE= adverse event; BP = blood pressure; con med = concomitant medications; CRU = clinical research unit; ECG = electrocardiogram; FU = Follow-up; HIV = human immunodeficiency virus; Hep = Hepatitis; PR = pulse rate; PK = pharmacokinetics; RR = respiratory rate.

*Day 3 is the completion visit. Assessments to be performed on Day 3 prior to discharge from the CRU or at early termination; physical exam, vital sign assessments, clinical laboratory tests and ECG.

¹A full physical exam will be conducted at screening and an abbreviated physical exam will be conducted on Day -1 and Day 3.

²Pre-dose and 1.5 h post infusion start ECGs will be triplicate ECGs (Triplicate ECGs will be performed approximately 1 minute apart).

³Clinical laboratory samples include: hematology, chemistry, coagulation parameters PT/INR/aPTT, and urinalysis.

⁴For female subjects – Serum pregnancy test at screening and urine pregnancy test at admission, both must be negative to enroll in the study.

⁵FSH and estradiol levels will be assessed in postmenopausal females to confirm status.

⁶IV infusion will occur at approximately 8:00 am, following completion of a low-fat breakfast. Infusion will over an approximately 60 minute period. Infusion stop time will have a time window of ± 5 minutes.

Time windows: Vital signs and ECGs: Pre-dose: within 60 min prior dosing; post-dose to ≤ 12 h: (± 15 min); ≥ 24 h: (± 30 min).

PK sampling: pre-dose (-60 min), < 2 h (± 5 min), 2 to < 24 h (± 10 min), 24, 36 and 48 h (± 15 min).

Injection site assessments: pre-dose (-60 min), ≤ 24 h (± 30 min).

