12.5 Pharmacokinetic Parameters

The plasma concentration time data for free tretinoin and liposome encapsulated tretinoin will be analyzed using non-compartmental methods. Actual dosing and sampling times will be used for PK analyses. The primary PK parameters of interest are: C_{max} , T_{max} , $t_{1/2}$, AUC_{last} . Additional PK parameters include AUC_{inf} , MRT, CL/F, V_zF and K_{el} .

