14.3 Pharmacokinetics

Pharmacokinetics:

Individual plasma concentrations and PK parameters of free tretinoin and liposome encapsulated tretinoin will be listed and summarized using descriptive statistics. Individual and mean free tretinoin and liposome encapsulated tretinoin concentration-time profiles will be presented graphically.

All PK parameters except T_{max} will be listed by treatment and subject, and summarized by treatment with descriptive statistics (n, mean [arithmetic and geometric], SD, min, median, max, and CV% [arithmetic, and geometric]). T_{max} will be described utilizing n, min, median, and max, and $t_{1/2}$ will be summarized using n, arithmetic mean and SD, CV%, min, median, and max.

A dose proportionality regression assessment for log-transformed C_{max} , AUC_{0-t} , and AUC_{0-inf} and log-transformed dose will be analyzed using a power model: $\ln(\text{PK parameter}) = \mu + \beta x \ln(\text{dose})$ for free tretinoin or liposome encapsulated tretinoin. The 90% confidence intervals (CI) around the slopes (β) from each of these regression analyses will be obtained from the model and presented. Plots of the log-PK parameter by log-dose (AUC_{0-t} , AUC_{0-inf} , and C_{max}) will be produced.

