### **5 Pharmacokinetic Analysis**

Plasma samples for the PK analysis of HF1K16 (free tretinoin and liposome encapsulated tretinoin) will be collected relative to Day 1 dosing.

Blood samples for plasma tretinoin and 4-oxotretinoin PK analysis will be collected within 60 minutes prior to start of infusion, and 0.5, 1, 1.5, 2, 4, 6, 9, 12, 24, 36, and 48 hours relative to start of infusion.

A deviation within allowable time windows will not be considered as a protocol deviation as long as the actual sampling time is recorded, refer to the following [Table 3](#) for allowed time window deviations.

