### 5.2 Pharmacokinetic Parameters

All PK calculations will be performed using Phoenix WinNonlin Version 8.1 (Certara USA, Inc., Princeton, USA). Plasma PK parameters for tretinoin and 4-oxotretinoin will be calculated with the IV infusion model non-compartmental analysis (NCA) with actual times of blood sample collection.

For PK parameter calculations, concentrations below BQL will be set to zero if they occur prior to the first or after the last quantifiable concentration and will be set to missing for data points in between.

Pharmacokinetic (PK) parameters  $AUC_{last}$ ,  $AUC_{inf}$ ,  $C_{max}$ ,  $T_{max}$ , MRT,  $K_{el}$ ,  $t_{1/2}$ ,  $CL/F$ , and  $V_zF$  for tretinoin and 4-oxotretinoin will be listed by treatment, subject and summarized by treatment with descriptive statistics as listed above for concentration data for the PK Population.

$AUC_{last}$  will be estimated using the linear trapezoidal method from time 0 hour to time  $t$ .  $AUC_{inf}$  will be calculated as the sum of  $AUC_{last}$  and  $AUC_{t-inf}$ , where  $t$  is the time corresponding to the last measurable serum concentration.  $AUC_{t-inf}$  will be calculated as  $C_t / \lambda_z$ , where  $C_t$  is the last measurable serum concentration and  $\lambda_z$  is the terminal phase rate constant. The value of  $\lambda_z$  will

be estimated by least-squares regression of the terminal log-linear serum concentration-time profile.

No value of  $K_{el}$ ,  $AUC_{inf}$ ,  $t_{1/2}$ ,  $V_zF$ , or  $CL/F$  will be reported for cases that do not exhibit a terminal log-linear phase in the concentration versus time profile with at least three timepoints. If the adjusted R-squared value (Rsq\_adjusted) is < 0.80, the PK analyst may evaluate if other time points are more appropriate for the calculation of  $\lambda_z$ , otherwise no value of  $K_{el}$ ,  $AUC_{inf}$ ,  $t_{1/2}$ ,  $V_zF$  and  $CL/F$  will be reported.

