### **5.3 Dose Proportionality**

For the dose cohorts Up to 3 mg/m^2, 6 mg/m^2, 10 mg/m^2, and 13 mg/m^2, a dose proportionality regression assessment for log-transformed  $C_{max}$ ,  $AUC_{0-last}$ , and  $AUC_{0-inf}$  and log-transformed dose will be analyzed using a power model:  $\ln(\text{PK parameter}) = \mu + \beta \times \ln(\text{dose})$  will be conducted for the free tretinoin and liposome encapsulated tretinoin. The 90% confidence intervals (CI) around the slopes ( $\beta$ ) from each of these regression analyses will be obtained from the model and presented. Plots of the log-PK parameter by log-dose ( $AUC_{last}$ ,  $AUC_{inf}$ , and  $C_{max}$ ) will be produced for the dose cohorts for the PK Population.

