### **9 Changes from pre-specified analyses**

There are no changes from the planned analyses for this study.

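### The synopsis calls for baseline-subtracted free tretinoin, but protocol 14.3 and SAP 5.1 to 5.3 have no subtraction step, so free-tretinoin AUC and half-life would be biased upward, by an unknown amount, if the endogenous level is quantifiable

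*Protocol*

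**What the plan says.** The protocol synopsis, under statistical methods for pharmacokinetics, reads: "Individual plasma concentrations and PK parameters of baseline-subtracted free tretinoin and liposome encapsulated tretinoin will be listed and summarized using descriptive statistics". The body of the protocol, section 14.3, has the same sentence without the qualifier: "Individual plasma concentrations and PK parameters of free tretinoin and liposome encapsulated tretinoin will be listed and summarized using descriptive statistics". The term occurs once and is not defined. The synopsis sentence on the power model does not say whether corrected or measured values feed the regression.

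SAP 3.2 lists concentrations as the laboratory delivers them. SAP 5.1 (summaries), 5.2 (non-compartmental analysis) and 5.3 (power model) set rules for BQL values, the trapezoid, the terminal slope and the regression, but none for an endogenous level. SAP 3.2 defines baseline as the last value on or before first treatment, for comparisons such as vital signs, and does not link it to PK. SAP 9 says: "There are no changes from the planned analyses for this study".

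Protocol 5.1 describes tretinoin as naturally occurring, at about 3 nM. SAP 5 schedules one pre-dose PK sample, within 60 minutes before the infusion.

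The analyte names also differ within the SAP. Section 5 opens with "Plasma samples for the PK analysis of HF1K16 (free tretinoin and liposome encapsulated tretinoin) will be collected relative to Day 1 dosing", and 5.3 says the power model "will be conducted for the free tretinoin and liposome encapsulated tretinoin". But 5.2 says "Plasma PK parameters for tretinoin and 4-oxotretinoin will be calculated with the IV infusion model non-compartmental analysis (NCA", and 3.2, 5.1 and the sampling sentence in section 5 use that second pair of names.

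**The concern.** Two analysts could follow these documents and produce different free-tretinoin tables. One working from the synopsis would subtract a baseline. One working from the SAP would not, because its BQL rule zeroes only values below quantitation, so a quantifiable pre-dose value enters the analysis as measured.

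An endogenous level left in the data adds a roughly fixed amount to every sample. That raises AUC, lowers CL/F and flattens the terminal phase, which lengthens the apparent half-life. The relative error is largest at the lowest dose. AUClast and half-life are two of the four PK parameters named as of primary interest, and they serve the secondary objective. Protocol section 14 says that the SAP will present any changes to the analyses proposed in the protocol and will be complete before unblinding. Leaving the choice open beyond that point would make it post hoc.

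**Working it through.** There is no figure in the plan to reproduce. The text comparison above establishes the contradiction without any assumption. What follows shows only the direction and possible range of the effect.

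**Endogenous level.** Protocol 5.1 gives about 3 nM. The molecular weight is 300.44 (C20H28O2, from the chemical name in the synopsis).
- 3 nmol/L × 300.44 g/mol = 0.901 ng/mL.
- 0.901 × 48 h = 43.3 ng*h/mL, if the level is flat and measured as free tretinoin.

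**Assumed model.** One compartment, 1-h infusion, dose-proportional, sampled at the SAP times (0, 0.5, 1, 1.5, 2, 4, 6, 9, 12, 24, 36, 48 h), linear trapezoid, constant 0.901 ng/mL added. With k = ln2/half-life, C(t) = Cmax(1−e^(−kt))/(1−e^(−k)) up to 1 h and Cmax·e^(−k(t−1)) afterwards. Human free exposure is not given, so Cmax at 3 mg/m² is set as a multiple of the baseline. Release from liposomes is not modelled.

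**AUClast at 3 mg/m².** Inflation = 43.3 / true AUC0-48.

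| True half-life | Cmax / baseline | True AUC0-48 (ng*h/mL) | Inflation |
|---|---|---|---|
| 2 h | 50 | 161 | +27% |
| 4 h | 50 | 299 | +14.5% |
| 12 h | 50 | 766 | +5.6% |
| 4 h | 200 | 1195 | +3.6% |
| 12 h | 200 | 3065 | +1.4% |
| 12 h | 1000 | about 15,320 (766 × 20) | +0.3% |

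At 13 mg/m² the true AUC is 13/3 times larger. The 4 h, 50-fold case falls from +14.5% to 14.5 × 3/13 = +3.3%. Cmax changes by at most 1/50 = 2% in all these cases.

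**Half-life.** True value 4 h, Cmax 50 times baseline, 3 mg/m², uncorrected. The answer depends on the points fitted:

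| Points fitted | Half-life | Adjusted R² |
|---|---|---|
| 2–12 h | 4.25 h | 1.00 |
| 6–24 h | 5.2 h | 0.99 |
| 1.5–48 h | 7.8 h | 0.90 |
| 24–48 h | 25.9 h | 0.72 |

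With the 1.5–48 h fit, AUCinf is +17.9%, so CL/F is 1/1.179 − 1 = −15.2%.

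**Does the adjusted R² < 0.80 rule in SAP 5.2 catch it?** Sometimes. Choosing points by maximum adjusted R², a true half-life of 2 h at 50-fold gives 0.67–0.77 across the four doses, which is flagged. A true half-life of 4 h gives 0.90 or more, which is not.

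**Dose-proportionality slope.** Regress ln(A·d/3 + 43.3) on ln(d) for d = 3, 6, 10, 13, where A is the true free AUC at 3 mg/m² and the true slope is 1.
- A = 1000 gives 0.98; 500 gives 0.96; 100 gives 0.82; 50 gives 0.70.
- For 24 active subjects the sum of squares of ln(dose) is 7.51. The 90% CI half-width is t(0.95, 22) × √ln(1+CV²) / √7.51 = 0.18 at an assumed CV of 30%, or 0.30 at 50%.
- The bias reaches the half-width only when A is as low as roughly 100 (30% CV) or 50 (50% CV) ng*h/mL.

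**Escalation cap.** 43.3 / 16550 = 0.26%.

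**The case against.** The strongest case on the other side is that this is one undefined word in a synopsis. The SAP agrees with protocol 14.3, so SAP 9 is wrong only if the synopsis governs, and the word could be a stray. It stands that the documents do not show which was intended. A reader might infer that a settled rule was knowingly dropped; the text does not support that. Protocol 12.5 ("The plasma concentration time data for free tretinoin and liposome encapsulated tretinoin will be analyzed using non-compartmental methods") is no independent evidence of a dropped rule either, since it matches the synopsis's own non-compartmental sentence, which also lacks the term.

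On size, a reader might infer that half-life would roughly double, or appear to fall with dose. In the 4 h, 50-fold case, the maximum adjusted R² choice of points does read 7.8, 6.6, 6.0 and 5.7 h from the lowest to the highest dose. But SAP 5.2 does not prescribe that choice, and the 2–12 h points from the same 3 mg/m² profile give 4.25 h. Nor can one say that the 0.80 rule misses the problem in general: protocol 5.1 calls the circulating half-life of tretinoin very short, and at short half-lives the rule does trigger. The exposure multiples are also arbitrary. The other concentration in protocol 5.1, about 1 µM, is about 333 times baseline (1000/3), where AUClast at a 4 h half-life is only 2.2% too high. Protocol 5.1 does not say that the 3 nM is in plasma, free or constant.

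These objections limit the size and rule out a claim about intent. They leave the contradiction, and the direction of the bias when the baseline is quantifiable, intact.

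**Conclusion.** The contradiction holds on the current text. An analyst following the SAP exactly would leave any quantifiable endogenous tretinoin in the free-tretinoin results, biasing AUC and half-life upward and CL/F downward, most at 3 mg/m².

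The size cannot be fixed from the documents. Under the assumed model, with Cmax at 3 mg/m² 50 to 1000 times baseline and half-life 2 to 12 h, AUClast inflation at that dose runs from about +27% to +0.3%. If the pre-dose value is BQL, corrected and uncorrected results coincide and the contradiction has no practical effect. The half-life error has no single value, because it depends on the terminal points selected.

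A reader might go further and infer that dose proportionality or dose escalation is compromised. The figures do not support that: slope bias is usually inside the 90% CI, and the cap is affected by 0.26%. This should be corrected, but it does not threaten the primary safety objective. The analyte-name mismatch is a separate defect that does not depend on the LLOQ.

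**What to change.** Make the passages agree before unblinding. Preferably, carry the synopsis rule into protocol 14.3 and SAP 5.1 to 5.3:

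- Derive free-tretinoin non-compartmental parameters and the power model from each concentration minus the subject's own pre-dose value.
- Take a BQL pre-dose value as zero.
- Handle corrected values at or below zero under the SAP 5.2 BQL rule: zero before the first or after the last quantifiable value, while those inside the profile "will be set to missing for data points in between".
- Show uncorrected results alongside.
- State whether encapsulated tretinoin is also corrected.

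If no correction is intended, delete the term from the synopsis or declare the departure in SAP 9. Separately, use one set of analyte names throughout SAP 3.2 and 5 to 5.3, matching the protocol, and say whether 4-oxotretinoin is an additional analyte.

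The cost is a few sentences and one derived variable; the pre-dose sample is already collected. The downside is that assay noise in one pre-dose value enters every corrected value. In the 4 h, 50-fold case, a 20% error in that value leaves 0.2 × 43.3 = 8.7 ng*h/mL in place of 43.3. Corrected half-life, with points chosen by maximum adjusted R², then reads 3.7 to 5.6 h, against 7.8 h uncorrected. Subtraction also cannot remove an endogenous level that lies below the LLOQ.
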